5.2 Exclusion Criteria

Participants are excluded from the study if any of the following criteria apply:

Category	Criterion
Medical Conditions	1. Pregnancy or currently in lactation
	2. Known hypersensitivity to any of the study intervention ingredients.
Prior/Concomitant Therapy	3. For participants reinitiating treatment with bintrafusp alfa at study entry: have received any systemic anticancer therapies/treatments since discontinuing bintrafusp alfa treatment. 4. Concurrent treatment with prohibited drugs (see Section 6.5.3)
Prior/Concurrent Clinical Study Experience	5. Participant has withdrawn consent from the parent study for any reason
Other Exclusions	6. Any other reason that, in the opinion of the Investigator, precludes the participant from participating in the study.

5.3 Lifestyle Considerations

5.3.1 Meals and Dietary Restrictions

There are no dietary restrictions.

5.4 Screen Failures

The Investigator will maintain an eligibility log to record details of all participants, to confirm eligibility, and if applicable, record reasons for exclusion.

6 Study Intervention(s)

Study intervention is any investigational intervention(s), marketed product(s), placebo, or medical device(s) intended to be administered to a study participant per the study protocol.

6.1 Study Intervention(s) Administration

Bintrafusp alfa will be administered as a monotherapy in this rollover study (see [Table 4](#)).

Table 4 Study Intervention

Intervention Name	Bintrafusp alfa
Type	Drug
Dose Formulation^a	Sterile concentrate solution for infusion
Unit Dose Strength(s)	10 mg/mL in single-use glass vials (600 mg provided per vial)
Dose Amount	
 • 1200 mg • 2400 mg • Other dose amount as specified in the participant's parent protocol
Frequency	
 • 1200 mg: once every 2 weeks • 2400 mg: once every 2 weeks • 2400 mg: once every 3 weeks • Other dose amount as specified in the participant's parent protocol: once every 2 weeks
Route of Administration	Intravenous infusion
Dosing Instructions	
 • Flat dose of 1200 mg administered over 1 hour (-10/+20 minutes, i.e., over 50 to 80 minutes) once every 2 weeks. • Flat dose of 2400 mg administered over a minimum of 1 hour (-10/+20 minutes) and up to 2 hours (-10/+20 minutes) once every 3 weeks. • Flat dose of 2400 mg administered over a minimum of 1 hour (-10/+20 minutes) and up to 2 hours (-10/+20 minutes) once every 2 weeks • Other dose amount, as specified in the participant's parent protocol, administered over 1 hour (-10/+20 minutes, i.e., over 50 to 80 minutes) once every 2 weeks.
Use	Experimental
Sourcing	Provided centrally by the Sponsor
Packaging and Labeling	Study Intervention will be provided in vial. Each vial will be packaged and labeled per all applicable regulatory requirements and Good Manufacturing Practice Guidelines.

6.2 Study Intervention(s) Preparation, Handling, Storage, and Accountability

The Investigator, institution, or the head of the medical institution (where applicable) is responsible for study intervention accountability, reconciliation, and record maintenance (i.e., receipt, reconciliation, and final disposition records).

- Upon receipt of the study intervention(s), the Investigator or designee will confirm appropriate temperature conditions have been maintained during transit and any discrepancies are reported and resolved before use. Also, the responsible person will check for accurate delivery. Further guidance and information for study intervention accountability are provided in the Pharmacy Manual.
- Only participants enrolled in the study may receive study intervention(s) and only authorized site staff may supply it. All study intervention(s) will be stored in a secure, environmentally controlled, and monitored (manual or automated) area, per the labeled storage conditions, and with access limited to the Investigator and authorized site staff.

- Dispensing will be recorded on the appropriate accountability forms so that accurate records will be available for verification at each monitoring visit.
- Study intervention(s) accountability records at the study site will include the following:
 - Confirmation of receipt, in good condition and in the defined temperature range.
 - The inventory provided for the clinical study and prepared at the site.
 - The dose(s) each participant used during the study.
 - The disposition (including return, if applicable) of any unused study intervention(s).
 - Dates, quantities, batch numbers, vial numbers, expiry dates, formulations for study interventions prepared at the site, and the participant numbers.
- The Investigator site will maintain records, which adequately documents that participants were provided the doses specified in this protocol, and all study intervention(s) provided were fully reconciled.
- Unused study intervention(s) will not be discarded or used for any purpose other than the present study. No study intervention that is dispensed to a participant may be re-dispensed to a different participant.
- Destruction of used and unused study intervention(s) should be performed at the site if allowed by local law only after Sponsor authorization. If that is not possible, the Sponsor/designee will be responsible for the destruction process.
- A Study Monitor will periodically collect the study intervention(s) accountability forms.
- Further guidance and information for the final disposition of unused study intervention(s) are provided in the Pharmacy Manual
- Bintrafusp alfa should be stored in a refrigerator (2°C to 8°C) until use. Bintrafusp alfa must not be frozen and should be stored in the original packaging.
- Additional instructions for the preparation, handling, storage, and disposal of bintrafusp alfa will be provided in the Pharmacy Manual.

6.3 Measures to Minimize Bias: Study Intervention Assignment and Blinding

6.3.1 Study Intervention Assignment

Sites will be required to discontinue participants in the parent study Interactive Web Response System (IWRS) before contacting the rollover study IWRS for enrollment. The rollover study IWRS will assign new unique patient identifiers number to participants in chronological order at the time of informed consent signature for parent study participants continuing in the rollover study.

6.3.2 Blinding

Blinding Method

This is an open-label, single-arm study; thus, study intervention is not blinded to participants or Investigators.

Assignment Method Retention

Not applicable, as this is an open-label study and blinding will not be used.

6.3.3 Emergency Unblinding

Not applicable.

6.4 Study Intervention Compliance

In this study, participants will receive study intervention at the study site. When participants are dosed at the site, they will receive study intervention directly from the Investigator or designee, under medical supervision. The date and time of each dose administered in the clinic will be recorded in the source documents and recorded in the electronic case report form (eCRF). The dose of study intervention and study participant identification will be confirmed at the time of dosing by a member of the study site staff other than the person administering the study intervention.

A record of the number of bintrafusp alfa vials dispensed to and taken by each participant will be maintained and reconciled with study intervention and compliance records. Intervention start and stop dates, including dates for intervention delays and/or dose reductions will also be recorded in the CRF.

Noncompliance is defined as a participant missing > 1 consecutive infusion of study intervention for nonmedical reasons and barring any extenuating circumstances in the opinion of the Investigator. Extenuating circumstances should be documented, and when possible, discussed with the Sponsor in advance. If > 1 infusion is missed and the interval between the subsequent infusion and the last administered treatment is longer than 6 weeks for nonmedical reasons, the criterion of insufficient compliance is met as well.

Consequences of noncompliance may lead to discontinuation of study interventions as described in Section 7.1. In case of overdose, see Section 8.4.

6.5 Concomitant Therapy

Record in the CRF all concomitant therapies (e.g., medicines or nondrug interventions) used from the time the participant signs the informed consent until completion of the study, including any changes. For prescription and over-the-counter medicines, vaccines, vitamins, and herbal supplements, record the name, reason for use, dates administered, and dosing information.

Any additional concomitant therapy that becomes necessary during the study and any change to concomitant drugs must be recorded in the corresponding section of the electronic eCRF, noting the name, dose, duration, and indication of each drug.

Contact the Medical Monitor for any questions on concomitant or prior therapy.

6.5.1 **Rescue Medicine**

Not applicable

6.5.2 **Permitted Medicines**

The only permitted medications are the following:

1. Any medications (other than prohibited in [Section 6.5.3](#)) that are considered necessary for the participants' welfare and will not interfere with the study intervention may be given at the Investigator's discretion.
2. Other drugs to be used for non-steroid premedication (antihistamine and acetaminophen) for the treatment of anaphylactic reactions, IRRs, and severe hypersensitivity reactions/flu-like symptoms and irAEs (see [Section 8.3.6](#)). Note that premedication should be administered prior to bintrafusp alfa dosing and should be based upon clinical judgment and presence and severity of prior infusion reactions
3. Blood transfusions and erythroid growth factors are permitted as clinically indicated.

Any medicines that are considered necessary to protect the participant's welfare in emergencies may be given at the Investigator's discretion, regardless if it results in a protocol deviation.

6.5.3 **Prohibited Medicines**

The following treatments must not be administered within 14 days before the start of study intervention or throughout the duration of study intervention. If the administration of a nonpermitted concomitant drug becomes necessary during the study, the participant will be withdrawn from study intervention (the Sponsor may be contacted to discuss whether the study intervention must be discontinued).

- Immunotherapy, immunosuppressive drugs (e.g., chemotherapy or systemic corticosteroids), or other experimental pharmaceutical products are prohibited (prior administration of bintrafusp alfa in an eligible parent study within 14 days before enrollment in this rollover study is allowed). Exceptions are allowed for short-term treatment of allergic reactions or for the treatment of irAEs, specifically:
- Short term administration of systemic steroid (i.e., for allergic reactions, for prophylaxis and management of radiographic contrast allergy or the management of irAEs and other AEs) is allowed.
- Steroids with no or minimal systemic effect (topical, intranasal, intro-ocular, inhalation) are allowed.
- Hormone replacement with corticosteroids for adrenal insufficiency is allowed if the steroids are administered only for the purpose of hormonal replacement and at doses ≤ 10 mg or equivalent prednisone per day.
- Prophylactic use of corticosteroids for IRRs is prohibited.

- Concomitant local or regional treatment (radio/chemo-embolization) is prohibited.
- Other systemic anti-cancer therapy.
- Live vaccines are prohibited. Administration of inactivated vaccines (e.g., inactivated influenza vaccines) or approved SARS-COV-2 vaccines is allowed.
- Any traditional Chinese medication used as anticancer treatment (regardless of the type of cancer) is prohibited. Traditional Chinese medication for indications other than anticancer treatment, such as supportive care, may be administered at the discretion of the Investigator.
- Herbal remedies with immunostimulating properties (e.g., mistletoe extract) or known to potentially interfere with major organ function (e.g., hypericin).

Medications other than those specifically excluded in this study (see above) may be administered for the management of symptoms associated with the administration of bintrafusp alfa as required. These might include analgesics, anti-nausea medications, antihistamines, diuretics, antianxiety medications, and medication for pain management, including narcotic agents.

6.5.4 Other Interventions

Palliative organ-sparing radiotherapy may be administered only for specific clinical indications during the study treatment period. The assessment of progressive disease (PD) will be made according to RECIST v1.1 and not based on the necessity for palliative radiotherapy.

6.6 Dose Selection and Modification

The doses and treatment schedules for bintrafusp alfa in this study were selected based on those used in the parent studies (see Section 4.1, Section 4.3, and Section 6.1 for details).

For participants who are continuing treatment with bintrafusp alfa and were previously assigned to a bintrafusp alfa dose based on body weight (i.e., a mg/kg dose) in a parent protocol, the Sponsor recommends switching to a flat dose of bintrafusp alfa 1200 mg every 2 weeks as they enroll in the rollover study, in consultation with the Sponsor Medical Lead. Otherwise, dose modification of bintrafusp alfa is not allowed except for management of bleeding AEs.

Modifications of the infusion rate due to IRRs are described in Section 7.1.

Doses cannot be delayed beyond the treatment window (\pm 3 days). Participants must skip the dose if the treatment window is missed. Every attempt should be made to perform applicable assessments in [Table 1](#) for any missed visits. Complete the next visit following the SoA (see [Table 1](#)).

6.7 Reinitiation Criteria

For participants who discontinue bintrafusp alfa treatment during this rollover study, one reinitiating course of treatment at the same dose and schedule is allowed at the discretion of the Investigator and with agreement of the Study Medical Responsible:

- Participants who enter into this rollover study on active treatment will be eligible for one reinitiating course of treatment during this rollover study, regardless of whether or not they reinitiated treatment in a parent study.
- Participants who reinitiate treatment with bintrafusp alfa at study entry into this rollover study will be eligible for one more reinitiation (second reinitiation) if treatment is discontinued during this rollover study.

The following participants are eligible for reinitiation:

- Participants who are experiencing a CR, a PR, or SD at the time of treatment discontinuation in the rollover study, and then subsequently develop disease progression after stopping therapy, but prior to the end of the study.
- Participants who discontinue from treatment in the rollover study due to an AE that is subsequently well managed or resolved, as assessed by the Investigator, prior to the end of the study.

The participant should reinitiate treatment at the treatment phase visit where they left off according to the SoA (see Section 1.3). Participants who reinitiate treatment should stay on study and should be treated and monitored according the SoA for the rest of the study.

Prior to reinitiation, the Investigator will need to confirm that the benefit of reinitiating treatment outweighs any risk involved, such as that which led to initial treatment discontinuation. For participants with only SD at the time of discontinuation, the Investigator should confirm that no other reasonable treatment options are available. In addition, to be eligible for reinitiation, the participant must not have previously withdrawn consent for this study and should have been followed up with regular eCRF documented evaluation scans up to reinitiation of treatment.

A rebaseline scan must be performed prior to reinitiation of study intervention. Additionally, relevant safety laboratory assessments, including both full hematology and full chemistry results within 2 weeks, must be available and verified. The clinical Investigator will determine whether additional evaluation and work-up are required on a case-by-case basis.

6.8 Study Intervention after the End of the Study

After a participant has completed the study, has withdrawn consent, or has been withdrawn early, no further treatment is foreseen within the scope of this protocol. If required and in accordance with the study site's SOC, symptom-guided appropriate treatment may be administered per the generally accepted medical practice and depending on the participant's individual medical needs.

On withdrawal from the study, participants may receive care they and their physicians agree upon.

7

Discontinuation of Study Intervention and Participant Discontinuation/Withdrawal

7.1 Discontinuation of Study Intervention

Duration of study intervention/criteria for treatment discontinuation will follow guidelines stated in the respective parent protocols.

Participants from all studies except for Study MS200647_0005:

Participants (except those from Study MS200647_0005) who have experienced a confirmed CR should continue treatment for a maximum of 24 months after confirmation of response (at the discretion of the Investigator). If the Investigator believes that a participant with confirmed CR may benefit from treatment beyond 24 months, it may be permissible to continue treatment after discussion with the Medical Monitor and the Sponsor's Medical Responsible.

Participants with SD or PR who are receiving bintrafusp alfa should continue treatment until meeting criteria for discontinuation.

Participants from Study MS200647_0005:

For participants from Study MS200647_0005, study intervention will continue until unacceptable toxicity, confirmed PD assessed by Investigator (unless participant meets the criteria for study intervention beyond progression), or for up to 26 doses in total across both the MS200647_0005 parent and MS200647_0054 rollover studies since the completion of cCRT doses in the MS200647_0005 parent study, whichever occurs first.

All Participants:

Participants may be discontinued from study intervention for any of the following reasons, one reinitiating course of treatment may be allowed (see [Section 6.7](#)):

- A participant may discontinue from the study intervention at any time at his/her own request (i.e., withdrawal of consent), and without giving a reason.
- Occurrence of an exclusion criterion that is clinically relevant and affects the participant's safety, OR if discontinuation is considered necessary by the Investigator and/or Sponsor.
- A participant may be discontinued at any time at the discretion of the Investigator for safety, behavioral, compliance, or administrative reasons (e.g., disruption of operations due to natural disasters, interruption of laboratory or facility accreditation, participant moving to another country, resignation of key staff). (See [Sections 7.1](#) and [Section 8.3.6](#) for TEAEs and AESIs that require treatment discontinuation).
- PD per RECIST v1.1, with the exception that participants receiving treatment may continue post PD if the participant's Eastern Cooperative Oncology Group Performance Status (ECOG PS) has remained at least stable, and if in the opinion of the Investigator, the participant will benefit from continued treatment (See [Section 7.1.2](#)).
- Unacceptable toxicity

- Drug must not be given to a known pregnant participant (see to [Appendix 3](#))
- Use of a prohibited concomitant drug, as defined in [Section 6.5.3](#) if discontinuation is considered necessary by Investigator/Sponsor.

Any treatment-emergent AE, especially of Grade 4 or recurrent event of Grade 3, that is assessed as related to bintrafusp alfa may require treatment interruption or permanent discontinuation of bintrafusp alfa treatment.

Grade 4 treatment-related TEAEs: Any Grade 4 treatment-related TEAEs require permanent treatment discontinuation, except:

- a. Endocrinopathies that have been controlled by hormone replacement,
- b. Isolated laboratory values out of normal range that do not have any clinical correlation. Discuss with Medical Monitor regarding work-up, management, and treatment continuation versus hold versus discontinuation for isolated Grade 4 laboratory abnormalities,
- c. If an alternative explanation is identified for Grade 4 non tumor bleeding.

Grade 3 treatment-related TEAEs: Participants with any recurrent Grade 3 treatment-related TEAEs should be permanently discontinued. **Exceptions** may be considered for the following after discussion with Medical Monitor (see also relevant management guidance sections):

- a. Transient Grade 3 flu-like symptoms or fever that is controlled with medical management.
- b. Transient Grade 3 fatigue, local reactions, headache, nausea, emesis that resolves to Grade ≤ 1 or baseline.
- c. Tumor flare phenomenon defined as local pain, irritation, or rash localized at sites of known or suspected tumors.
- d. Any Grade ≥ 3 drug-related amylase or lipase abnormality that is not associated with symptoms or clinical manifestations of pancreatitis.
- e. Grade 3 hemoglobin (Hgb) decrease (< 8.0 g/dL) that is clinically manageable with blood transfusions or erythroid growth factor use.
- f. Increases ECOG PS ≥ 3 that resolves to ≤ 2 by Day 1 of the next infusion (i.e., infusions should not be given if the ECOG PS is ≥ 3 on the day of treatment and should be delayed until ECOG PS ≤ 2).
- g. Keratoacanthoma (KA) and cutaneous squamous cell carcinoma (cSCC).
- h. Grade 3 non tumor bleeding requiring intervention or hospitalization if alternative explanation can be identified (such as concomitant use of antithrombotic agents, traumatic event, etc.).

If persistent Grade 3 treatment-related AEs (excluding endocrinopathies controlled with hormone replacement therapy) either do not resolve or improve to Grade 1 within 12 weeks after last dose of study intervention, treatment must be permanently discontinued. If a Grade 2

treatment-related TEAE improves to Grade ≤ 1 or completely resolves by the day before the next infusion, study intervention may be continued.

Grade 2 treatment-related TEAE

If a Grade 2 treatment-related TEAE does not improve to Grade 1 or completely resolve by the day before the next infusion, but it is manageable and/or not clinically relevant, the Medical Monitor should be consulted to assess if it is clinically reasonable to administer the following infusion. In any case, if ≥ 2 doses are missed due to AE, the Medical Monitor should be consulted.

Immune-related AEs, IRRs, anemia, TGF β inhibition mediated skin reactions, and bleeding AEs

Permanent study intervention discontinuation may be recommended, so the relevant section must be reviewed:

- For suspected irAEs, general guidance and management are provided in [Section 8.3.6.2](#). Recommended guidance and management for specific irAEs as per published guidelines is provided in the current National Comprehensive Cancer Network (NCCN) guideline available at <http://www.nccn.org>.
- IRR and hypersensitivity reaction management guidance are presented in [Section 8.3.6.1](#).
- Anemia management guidance is presented in [Section 8.3.6.4](#).
- TGF β inhibition mediated skin reactions management guidance is provided in [Section 8.3.6.3](#).
- For guidance and management of bleeding AEs, see [Section 8.3.6.5](#).

If study intervention is permanently discontinued, the participant will remain in the study to be evaluated for the End of Treatment and Safety Follow-up. The Schedule of activity (see [Table 1](#)) indicates data to be collected at the time of discontinuation of study intervention and follow-up and for any further evaluations that need to be completed.

In case of discontinuation from the study intervention:

- The day of End of Treatment will correspond to the day of withdrawal (or within 7 days) for further details refer to [Table 1](#).
- An attempt should be made to perform all assessments scheduled for the End of Treatment visit if possible. If not possible, the most clinically relevant assessments and appropriate eCRFs for the End of Treatment visit should be prioritized as feasible.
- Participants will be asked to continue Safety and Survival Follow-up, which includes the collection of data on survival and subsequent anticancer therapy.
- If the participant is enrolled into a new study or any new therapy post-withdrawal from study intervention, the Safety Follow-up visit should be scheduled prior to the start of the new treatment irrespective of the 30-day Safety Follow-up period.
- Liver Injury:

The Investigator will consider discontinuation of study intervention for abnormal liver function if the Investigator believes that it is in best interest of the participant.

- Cardiac changes (e.g., QTc):

If a clinically significant finding is identified (including changes from baseline in QT interval corrected using Bazett's formula [QTcB] or Fridericia's formula [QTcF] after enrollment, the Investigator or qualified designee will determine if the participant can continue in the study and if any change in participant management is needed. This review of the electrocardiogram (ECG) printed at the time of collection will be documented. Any new clinically relevant finding is reported as an AE.

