8.3.6.5 Bleeding Adverse Events

Bleeding AEs are AESIs and considered important identified risk.

Mucosal/Non-tumor Bleeding

Participants treated with bintrafusp alfa were commonly reported with mild to moderate mucosal AEs such as epistaxis, hemoptysis, gingival bleeding and hematuria. In general, these reactions resolve without discontinuation of treatment.

For Grade 2 non-tumor bleeding, see Section 7 for general management of Grade 2 treatment-related TEAEs.

For Grade ≥ 3 non-tumor bleeding, study treatment must be permanently discontinued unless an alternative explanation can be identified (such as concomitant use of antithrombotic agents, traumatic event, etc.). In case of alternative explanations for the Grade ≥ 3 bleeding event, study treatment should be held until the event recovers to Grade ≤ 1 . If Grade ≥ 3 bleeding event is observed, regardless of causality with the study intervention, upon resumption of study intervention bintrafusp alfa dose should be reduced by 50% (600 mg once every 2 weeks for participants dosed with 1200 mg, 1200 mg once every 2 weeks for participants dosed with

2,400 mg). Once there is stable resolution and no recurrence of bleeding on reduced dose, Investigator is encouraged to communicate with Medical Monitor on potential dose re-escalation after careful benefit-risk assessment.

For Grade 4 non-tumor bleeding, treatment must be permanently discontinued if no alternative explanation is identified.

In case of rapid decrease of hemoglobin (Hgb), such as a decrease greater than 2.0 g/dL across a 2 weeks period (or 3.0 g/dL across a 3 week period), withhold the subsequent cycles of study intervention until Hgb is stabilized and do a thorough assessment of bleeding (for example, upper and lower GI endoscopy, enhancement CT etc.); if Grade 1 or greater bleeding is observed or suspected, withhold the bintrafusp alfa until the bleeding is resolved/controlled and resume the dose of bintrafusp alfa reduced by 50%. Once Hgb decrease is recovered to \leq Grade 1 or baseline and stably controlled, the Investigator is encouraged to communicate with Medical Monitor to re-escalate the dose. The dose of bintrafusp alfa may be re-escalated to full dose once Hgb is stabilized without further need for blood transfusion in the subsequent cycles. The timing of re escalation may need a case-by-case decision. See Section 8.3.6.4 regarding stabilization of anemia.

Tumor Bleeding

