Participants treated with bintrafusp alfa were reported in lower frequencies, with Grade \geq 3 hemorrhages including tumor bleeding. For Grade \geq 2 tumor bleeding, study treatment must be held until the event recovers to Grade \leq 1. If Grade \geq 3 bleeding event had been observed, regardless of causality with the study intervention, upon resumption of the study intervention bintrafusp alfa dose should be reduced by 50%. Once there is stable resolution and no recurrence of bleeding on reduced dose, Investigator is encouraged to communicate with Medical Monitor potential dose re-escalation after careful benefit-risk assessment. Treatment should be permanently discontinued if the Investigator considers the participant to be at risk for additional severe bleeding. In case of rapid decrease of Hgb, see Section 8.3.6.5 Mucosal/Non-tumor Bleeding.

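### Protocol Sections 7.1 and 8.3.6.5 are not expressly reconciled for treatment-related Grade 4 tumor bleeding, and the Section 5.1 exclusion cites Section 6.8, which holds no relevant rule

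*Protocol*

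**What the plan says.** **Stopping rule.** Protocol Section 7.1 sets a general rule by grade and causality: "Any Grade 4 treatment-related TEAEs require permanent treatment discontinuation, except" in cases a to c. Case a is an endocrinopathy controlled by hormone replacement. Case b is an isolated laboratory value without clinical correlation. Case c reads "If an alternative explanation is identified for Grade 4 non tumor bleeding". Section 7.1 also tells the reader to consult Section 8.3.6.5 for bleeding events, and opens by deferring to the parent protocols for discontinuation criteria.

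**Tumor bleeding.** Section 8.3.6.5 says that for Grade 2 or higher "tumor bleeding, study treatment must be held until the event recovers to Grade" 1 or lower. After Grade 3 or higher it adds, "regardless of causality with the study intervention, upon resumption of the study intervention bintrafusp alfa dose should be reduced by 50" per cent. On a permanent stop it says: "Treatment should be permanently discontinued if the Investigator considers the participant to be at risk for additional severe bleeding".

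**Entry.** Section 5.1 excludes people who had adverse events requiring permanent discontinuation, naming some immune-related and some bleeding events as examples. For details it refers to Sections 6.8 and 2.3.1. Section 6.8 describes care once a participant has left or completed the study. The bleeding row of Table 2 in Section 2.3.1 refers onward to Section 8.3.6.5.

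**The concern.** A related Grade 4 tumor bleed falls under both texts. Section 7.1 decides it by grade and causality. Section 8.3.6.5 describes a hold, a condition on resuming, and a permanent stop that turns on a forward-looking judgment of risk. A site working from the tumor-bleeding paragraph alone could re-treat after a life-threatening event that Section 7.1 makes a permanent stop, and could cite protocol text for doing so. Under SAP Section 10.2.1 the same participant might be recorded as an important deviation, because developing withdrawal criteria without being withdrawn is on that list.

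The entry exclusion has a related weakness. It turns on which events require permanent discontinuation, yet one of its two references leads to unrelated text and the other does not reach the Grade 4 rule. Section 5 permits no waivers of eligibility criteria, so a site should be able to find what the criterion means.

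**Working it through.** No arithmetic applies beyond counting. The check sets the two protocol sections side by side for each kind of Grade 4 bleed.

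| Grade 4 event | Section 7.1 | Section 8.3.6.5 | Do they fit? |
|---|---|---|---|
| Non-tumor, related, no other explanation | Permanent stop | Permanent stop, in a sentence specific to Grade 4 | Yes |
| Non-tumor, other explanation found | Exempt under case c | Hold, then a dose condition on resumption | Yes |
| Tumor, judged unrelated | Grade 4 rule does not apply | Hold, dose condition on resumption, judgment-based stop | Yes |
| Tumor, judged related | Permanent stop, no exception applies | Hold, dose condition on resumption, judgment-based stop | Not expressly reconciled |

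Counts behind the last row:

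- Exceptions to the Grade 4 rule: 3. Naming bleeding: 1 (case c, non-tumor). Covering tumor bleeding: 0.
- Grade 4-specific sentences in Section 8.3.6.5: 1 for non-tumor bleeding, 0 for tumor bleeding.

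The gap is therefore confined to one cell. For non-tumor bleeding the management section repeats the Grade 4 stop. For tumor bleeding it does not, and its wording has neither an upper grade limit nor a causality limit. If Section 7.1 has already settled a related Grade 4 tumor bleed, the Investigator's judgment in Section 8.3.6.5 has no role in that case, but the section does not say so.

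Following the two references in Section 5.1:

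- Section 6.8 contains no rule on adverse events or bleeding.
- Section 2.3.1 is on topic. Its bleeding row leads to Section 8.3.6.5, which holds the permanent-stop rules for non-tumor bleeding and the judgment-based stop for tumor bleeding. Its immune-related row leads to Section 8.3.6.2. Within 8.3.6.5 the only link back to Section 7 is for Grade 2 non-tumor bleeding, so the trail does not reach the Grade 4 rule.

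Section 7.1 itself, in its bullet on discontinuation at the Investigator's discretion, names Sections 7.1 and 8.3.6 as the places where stop-requiring events are found.

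**The case against.** The strongest reply is that the two sections work cumulatively. Stopping satisfies both. Section 8.3.6.5 does not order resumption; it sets a condition for when resumption happens, and it does not say its judgment-based stop is the only one. The Grade 4 rule is categorical with a closed list, and case c shows that Grade 4 bleeding was considered and only non-tumor bleeding exempted. Section 7.1 names itself and 8.3.6 jointly as sources of stops, and sends the reader to the management sections because a permanent stop may be advised there. The non-tumor text uses almost the same formula, "regardless of causality with the study intervention, upon resumption of study intervention bintrafusp alfa dose should be reduced by 50" per cent, beside a mandatory stop, so the formula alone does not displace a stop.

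Most of this stands. A reader might infer that the sections flatly contradict each other; they do not, because a coherent joint reading exists. It leaves the resumption wording to govern Grade 3 events that 7.1 does not itself stop and Grade 4 events judged unrelated. But that reading has to be inferred. No sentence ranks the sections, and the pointer in 7.1 can equally be taken to make 8.3.6.5 the specific rule.

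Three other stronger readings are not supported:

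- For a rapid hemoglobin fall, the tumor-bleeding text says "In case of rapid decrease of Hgb, see Section 8.3.6.5 Mucosal/Non-tumor Bleeding", and that paragraph says to "withhold the bintrafusp alfa until the bleeding is resolved/controlled and resume the dose of bintrafusp alfa reduced by 50" per cent. A reader might infer an order to resume after a bleed of any grade. Read that way, it would also override the Grade 4 non-tumor stop in the sentence just before it. It is more naturally read as hemoglobin management subject to the stop rules, so it is not evidence of conflict.
- A reader might infer that Section 6.7 contradicts the entry exclusion, because it allows re-initiation after a resolved or well-managed event. It is silent on events classed as permanent, which is not the same as inconsistent. It also requires the Investigator to confirm that benefit outweighs risk, and the Study Medical Responsible to agree.
- A reader might infer that Section 7.1 is certainly the intended target in Section 5.1. Entry after an adverse event also depends on the parent protocol permitting re-initiation, so parent-protocol criteria may govern too. Those protocols were not available.

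**Conclusion.** Two defects hold. First, no text expressly settles how Sections 7.1 and 8.3.6.5 combine for related Grade 4 tumor bleeding. Second, the reference to Section 6.8 in the Section 5.1 exclusion is wrong, and the remaining reference is indirect and does not reach the Grade 4 rule.

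The reach is narrow: related Grade 4 tumor bleeds that recover, and entry decisions about events of that kind. The protocol expects at least 10 participants and gives no rate for these bleeds, so no frequency is claimed. No planned estimate is shown to change: SAP Section 10.2.1 provides only a listing of important deviations, and Section 10.2.2 gives no reasons for exclusion from an analysis set.

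Safeguards lower the risk. Section 2.3 requires discussion with the Medical Monitor before enrollment when someone restarts after an adverse event, although Section 5.1 words that consultation as needed. The Sponsor has the final say on transfers (Sections 1.1 and 4.1). A clinical Grade 4 event must be reported as serious (Appendix 4), within 24 hours (Section 8.3.1). None of these says which text governs. The matter is worth fixing because these are operative safety-stop and eligibility rules for a risk that Section 2.3.1 classes as important and identified. The conclusion assumes that no parent protocol or site manual outside these documents already settles the order of precedence.

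**What to change.** - Reconcile Section 7.1 with the tumor-bleeding text of Section 8.3.6.5 so that one stated rule covers related Grade 4 tumor bleeding. Which rule is for the sponsor to decide. A sentence on precedence, or a Grade 4 sentence in the tumor-bleeding text to match the one for non-tumor bleeding, would make the choice visible.
- Replace the Section 6.8 reference in Section 5.1 with the section the sponsor intends. Section 7.1 already points to 7.1 and 8.3.6 for events that require discontinuation.
- Say in Section 5.1 whether parent-protocol discontinuation criteria also apply when judging the exclusion.
- Optionally, say in Section 6.7 whether events classed as requiring permanent discontinuation can be followed by re-initiation.

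The cost is protocol amendment wording and the approvals described in Appendix 2. Design, sample size and analysis are unchanged.
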